## 4. INVESTIGATIONAL PLAN

### 4.1 Overall Study Design

[figure not shown]
This global, multicenter study will be conducted in a randomized, sham procedure-controlled, parallel-group, subject-blinded fashion in approximately 70 adults CS subjects who have failed previous medical management and have not undergone ESS. Subjects enrolled in the study will include patients who have not had ESS but their symptoms are not adequately controlled on medical management and are seeking further treatment. This may include patients who are considering sinus surgery or those who have decided against it. The efficacy and safety of LYR-210 (2500 µg) and LYR-210 (7500 µg) versus a sham procedure only control will be assessed. Additionally, the study results of LYR-210 (2500 µg) and LYR-210 (7500 µg) will be compared to evaluate dose related responses.

The study will consist of three stages:

- Screening and Washout Stage: 2 - 4 weeks
- Randomized and Blinded Treatment Stage: 24 weeks
- Blinded Post-Treatment Follow-Up Stage: 24 weeks

The overall flow diagram of subject enrollment and follow up schedule is shown in Figure 1.

**Figure 1: Study Design Schematic**

#### **4.1.1 Screening Stage**

After providing written informed consent, subjects who are qualified to participate in this study will have an initial Screening visit. Immediately following the initial Screening visit, subjects will undergo a minimum of 2-week but a maximum of 4-week washout period. During this washout period, subjects will receive no active treatment for CS but are recommended to start daily saline irrigation twice a day. Subjects will be provided with saline and instructions for daily intranasal saline irrigations while participating in the study.

Medications that are prohibited during the washout period (and during the study) are listed in Section 6.4.2. Beginning at least 7 days prior to Day 1 visit, subjects will record the severity of the 4 cardinal symptoms of CS and the use of saline irrigation each day in the morning on the electronic subject reported outcomes (ePRO) questionnaire.

#### **4.1.2 Treatment Stage**

The total duration of the Treatment Stage will be 24 weeks. Subjects who complete the study Screening assessments and the washout period and meet all eligibility criteria on Day 1 will be stratified according to the presence or absence of nasal allergy and nasal polyps and, then, randomized in a 1:1:1 ratio to receive LYR-210 (2500 µg), LYR-210 (7500 µg), or sham procedure. Subjects who are assigned to the experimental arms will have the LYR-210 administered bilaterally into the middle meatus (Section 6.2) and, then, removed at Week 24 (Section 6.5). Subjects who are assigned to the sham procedure arm, will undergo bilateral mock administration (i.e., sham procedure) on Day 1. Enrolled subjects will undergo scheduled study visits at Weeks 2, 4, 12, and 24 during the treatment duration. Subjects will receive phone follow-ups at Weeks 8, 16, and 20 to record AEs and concomitant medications/procedures that they have had since last follow-up assessment. [NOTE: Female subjects of childbearing potential will be asked to return to the clinic for urine pregnancy test at Weeks 8, 16, and 20.] All subjects will remain blinded and undergo the assessments and procedures scheduled for these visits (Section 8.1).

At the Week 24 visit, all subjects will return to clinic for the **end-of-treatment (EOT)** visit assessments. Subjects who receive LYR-210 will have bilateral depot removed using standard surgical tools. Sham control subjects will undergo a sham removal procedure to remain blinded.

If medically warranted per the treating physician's discretion (for example, needing an ESS as rescue treatment), early depot removal before the schedule EOT visit at Week 24 may be performed at an unscheduled **early-termination (ET)** visit (an unscheduled EOT visit). Any subject who undergoes an ET visit is required to complete the assessments scheduled for the Week 24/EOT visit, and all safety follow up visits post treatment.

If spontaneous dislodgement of LYR-210 occurs before Week 24 in subjects who receive either dose of LYR-210, subjects are required to call the study clinic immediately to report the event. If

a subject experiences a dislodgement of one of the two LYR-210 depots, the subject will continue the study treatment unless an early treatment discontinuation is recommended by the treating physician or subject requests depot removal from the remaining side of the nose. If depots spontaneously dislodge from both sides of the nose, subject will complete Week 24/EOT assessments and subsequently, the post-treatment follow-up stage.

#### **4.1.3 Post-Treatment Follow-Up Stage**

After the Week 24/EOT visit, all enrolled subjects will undergo a blinded Post-treatment Follow-up Stage that will be approximately 24 weeks. Subjects will have 2 additional scheduled safety follow up visits, the Week 28 and a final Week 48/EOS visit. Subjects will receive phone follow-ups at Weeks 32, 36, 40, and 44 to record AE and concomitant medications/procedures that they have had since last follow-up assessment. Except for the cases of depot dislodgement, subjects should remain blinded until the study database is locked.

#### **4.1.4 End of the Trial**

The end of the trial is defined as the date of the last EOS visit of the last subject of the study.

### **4.2 Rationale for Study Design**

The goal of treatment is to reduce the symptoms of adult CS with a well-tolerated product. The study design and endpoints are adequate for assessment of safety and efficacy of LYR-210 in the context of a Phase II study of subjects with CS. Blinding and randomization will reduce the potential for treatment and assessment bias and will improve the veracity of detected safety and efficacy, particularly in the use of self-reported ePRO instruments for assessment of CS symptoms. The parallel arm study design and 1:1:1 randomization scheme of LYR-210 (2500 µg): LYR-210 (7500 µg): sham procedure permits adequate statistical comparison of groups for efficacy assessment and safety signal detection. The ePRO of daily morning cardinal symptoms and the SNOT-22 subject reporting instruments have been selected because they are specific to the subject population to be enrolled in this study. Other efficacy endpoints involving objective changes in the sino-nasal cavities (i.e., inflammation and polyps), smell dysfunction improvement, and general quality of life improvement are appropriate for development and further refinement of study endpoints in the clinical program. Although MF is well-characterized as a treatment in other indications, chronic assessments of local nasal and ophthalmologic parameters in this study's CS population and in the context of in situ delivery via drug-depot are appropriate for associating safety results with local MF levels. Summarized in Section 9.1 is the safety rationale for the selection of drug doses and polymers in LYR-210 in this Phase II study.

### **4.3 Discontinuation of Study Subjects**

Subjects will be encouraged to complete the study through the treatment and post-treatment follow up periods. Each subject is free to discontinue from the study at any time, for any reason, and without penalty or loss of benefit. Participation in the study treatment may be discontinued for any of the following reasons:

- Occurrence of any medical condition or circumstance that exposes the subject to substantial risk and/or does not allow the subject to adhere to the requirements of the protocol, including early removal of LYR-210 (Section 6.5).
- Any serious AE (SAE, Section 8.4.9.2), clinically significant AE, severe laboratory abnormality, intercurrent illness, or other medical condition that indicates to the Investigator that continued participation is not in the best interest of the subject.
- Subject's decision to withdraw.
- Requiring ESS as rescue treatment.
- If deviations to the use of prohibited medications occur after randomization and study treatment, the Investigator in consultation with the Sponsor and Sponsor's medical monitor will decide on a case-by-case basis whether the subject may continue in the study based on the time the prohibited medication was administered and its pharmacology.
- Subject's failure to comply with protocol requirements or study related procedures.
- Termination of the study by the Sponsor or a regulatory authority that has provided approval to proceed.

Subjects who withdraw or are withdrawn from the study treatment will be requested to return to the clinic for the assessments and procedures scheduled for the EOT visit and the safety follow up visits post EOT (Section 8.1).

The Investigator or study staff will document the reason(s) for subject discontinuation on the Case Report form (CRF), notify the IRB/EC as required by their Institution's procedures, and notify the Sponsor the reason for discontinuation.

#### **4.4 Criteria for Study Termination**

If the Sponsor, the Investigator, the medical monitor, the data monitoring committee (DMC), Institutional Review Board (IRB)/Ethics Committee (EC), and/or appropriate regulatory officials discover conditions arising during the study that indicate the study should be halted or that the study center should be terminated, appropriate action may be taken after consultation among (at a minimum) the Sponsor, the IRB/EC, and the medical monitor. Refer to Section 11.13 for additional information.

#### **4.5 Data Monitoring Committee (DMC)**

An independent DMC will be formed by charter to assist in examining safety data periodically during the study and will include independent physicians with appropriate experience of clinical trials but who are not participating in this study. The DMC will:

- Review the safety and tolerability data at predefined time points. The first study level safety review will occur after the 30th subject has completed 4 weeks of treatment or early terminated from the study, whichever occurs first. A second safety review will occur after all enrolled subjects have completed the Week 4 follow-up. The timing and details of subsequent data review will be detailed in the DMC charter.

- Review the safety data at *ad hoc* time points if significant safety concerns are identified during the study.
- Review events that may impact subject continuation and make recommendations regarding study progression.
- Review any other data, as appropriate.

The membership, responsibilities and operating procedures of the DMC will be described in a DMC Charter.

## **5. SELECTION OF SUBJECTS**

### **5.1 Subject Screening**

All subjects evaluated for participation in this study will be screened for study eligibility. A delegated member of the Institution's research team will review the subject's medical history to screen for study eligibility. All subjects who meet initial eligibility requirements will be asked to participate in the study. Each subject will indicate his or her willingness to participate in the study by signing an IRB/EC-approved informed consent form (ICF).

Each subject will be assigned a unique subject identification number upon signing informed consent. Subjects who are assigned a subject ID but do not meet the eligibility criteria will be considered Screen Failures.

If the Investigator believes rescreening is warranted, a subject can be rescreened upon consultation with the study Medical Monitor or study Sponsor. Subject numbers assigned to subjects who fail screening should not be reused. Investigators must account for all subjects who sign an ICF. If the subject is found to be not eligible at this visit, the investigator/designee should still complete the applicable electronic case report forms (eCRF).

### **5.2 Subject Informed Consent**

Prior to enrollment in the study, all subjects must review and complete an IRB/EC-approved ICF. All potential subjects must complete the consent process prior to undergoing procedures performed specifically for this study that are outside the standard of care for the institution. Failure to obtain a signed ICF renders the subject ineligible for the study. Sites will comply with ICH Guidelines for obtaining informed consent.

### **5.3 Inclusion Criteria**

A subject must meet all of the following criteria to be eligible for this study:

1. Age  $\geq$  18.
2. A CS subject who
  - a. has twelve weeks or longer of two or more of the following symptoms:
    - nasal blockage/obstruction/congestion
    - nasal discharge (anterior, posterior, or both)
    - facial pain/pressure
    - reduction/loss of sense of smell

and one or more of the following findings:

- evidence of inflammation within paranasal sinuses or ostiomeatal complex on MRI

- evidence of purulence coming from paranasal sinuses or ostiomeatal complex
  - nasal polyps
- b. has a composite score of 7-day average scores of 4 CS cardinal symptoms  (CS7DA4S)  $\geq 7$  (0-3 scale for each of the symptoms) at Day 1 visit, and
  - c. has had at least two trials of medical treatments in the past, one of which must include intranasal corticosteroid sprays (INCS) for a minimum of 4 weeks.
3. Must be able to cease treatment with intranasal corticosteroid and decongestant sprays at Screening.
  4. Ability to tolerate topical anesthesia.
  5. Has been informed of the nature of the study and has provided written informed consent as approved by the IRB/ EC of the respective clinical site or regulatory authority if applicable by national law.
  6. Agrees to comply with all study requirements.

#### 5.4 Exclusion Criteria

A subject who meets any of the following criteria will be excluded from this study:

1. With previous balloon sinuplasty or any endo-nasal surgery (including sinus surgery), except for septoplasty or surgical manipulation to nasal turbinates more than 6 months prior to the Screening visit.
2. Seasonal allergic rhinitis (SAR) subjects with symptoms and/or, based on time of year, would anticipate onset of symptoms within 4 weeks of randomization.
3. Perennial allergic rhinitis (PAR) subjects whose symptoms are well controlled by regular use of intranasal corticosteroids.
4. With severe asthma or with one or more exacerbations of asthma requiring systemic corticosteroid use within the 6 months prior to the Screening visit. Subjects with moderate or severe asthma will also be excluded if they have not been on a stable regimen of inhaled corticosteroids for asthma for a minimum of 3 months prior to the Screening visit.
5. Endoscopic exclusion criteria:
  - a. Complete/near complete middle meatal obstruction preventing proper placement and/or visualization of LYR-210.
  - b. Evidence of mucosal erosion or ulceration.
  - c. Ongoing nasal infection.
  - d. Evidence of nasal septal perforation.
6. MRI exclusion criteria:
  - a. A bilateral Zinreich score  $< 4$  in all 3 pairs of the posterior ethmoid, frontal, or sphenoid sinuses (0-5 scale for each of the sinuses) on Screening MRI.

- b. Anatomic variation which, in the opinion of the Investigator, would adversely impact placement of LYR-210.
  - c. Structural, non-inflammatory related CS (e.g., large concha bullosa, tumor).
  - d. Sinus disease extended into orbital or intracranial space.
  - e. Evidence of mycetoma/fungal ball, allergic fungal rhinosinusitis.
  - f. Sinus mucocele.
7. History or clinical evidence or suspicion of invasive fungal sinusitis, allergic fungal rhinosinusitis, or atrophic rhinitis.
  8. Known history of hypersensitivity or intolerance to corticosteroids.
  9. Oral-steroid or monoclonal antibody (Xolair, Nucala) dependent condition.
  10. Having had systemic corticosteroids within 1 month prior to Screening visit.
  11. Known history of hypothalamic pituitary adrenal axial dysfunction or having a clinically significant out of normal range morning serum cortisol level at screening.
  12. Previous pituitary or adrenal surgery.
  13. Has had more than 1 episode of epistaxis with frank bleeding requiring medical attention within 2 months of Screening visit or more than 1 episode of epistaxis with frank bleeding within 1 month of Screening visit.
  14. Has had acute exacerbation of nasal allergy or chronic sinusitis, upper respiratory tract infection (URTI), or common cold within 4 weeks of the Screening visit.
  15. Had dental procedure/implant on maxillary dentition within 4 weeks of the Screening visit.
  16. Has past or present acute or chronic intracranial or orbital complications of CS (e.g., brain abscess, related problems with eyes or central nervous system).
  17. History or diagnosis (in either eye) of glaucoma or ocular hypertension (IOP > 21 mmHg).
  18. With prior cataract surgery or presence (in either eye) of posterior subcapsular cataract of grade 2 or higher, nuclear sclerosis of grade 3 or higher, or cortical cataract of grade 2 or higher or involving a minimum of center optic zone of 3 mm diameter.
  19. Past or present functional vision in only one eye.
  20. Diagnosed with ongoing rhinitis medicamentosa.
  21. Known history of immune dysfunction including immune deficiency (IgG subclass deficiency or IgA deficiency) or autoimmune disease (e.g., Wegener's granulomatosis, sarcoidosis).
  22. Past, present, or planned organ transplant or chemotherapy with immunosuppression.
  23. History or diagnosis of ciliary dysfunction (e.g., cystic fibrosis, primary ciliary dyskinesia [Kartagener syndrome]).
  24. Past or present systemic vasculitis (e.g., granulomatosis with polyangiitis).

25. Evidence of disease or condition expected to compromise survival or ability to complete follow-up assessments.
26. Pregnant or breast feeding. Females of child-bearing potential must test negative for pregnancy at the time of screening based on a serum pregnancy test and reverified at the time of enrollment based on a urine pregnancy test. Both male and female subjects of reproductive potential must agree to use highly effective methods of birth control, throughout the study.
27. Previously participated in LYR-210 Phase I clinical study or received an experimental treatment in another clinical study within 5 half-lives of Screening visit.
28. Currently participating in an investigational drug or device study.
29. Determined by the Investigator as not suitable to be enrolled for reasons not already specified if the health of the subject or the validity of the study outcomes may be compromised.

## **6. TREATMENT OF SUBJECTS**

### **6.1 Randomization**

Subjects who complete the study Screening assessments and the washout period, and meet all eligibility criteria on Day 1 will be, before any treatment, randomized in a 1:1:1 ratio to one of the following study arms:

- Arm 1: bilateral administration of LYR-210 (2500 µg)
- Arm 2: bilateral administration of LYR-210 (7500 µg)
- Control Arm: bilateral sham procedure

Subjects will be stratified for treatment assignment according to the following criteria:

- Nasal allergy (Yes vs No)
- Nasal polyps (Yes vs No)

For any reason, if the Investigator is unable to successfully administer LYR-210 or perform sham procedure into both middle meatuses in a subject (as described in Section 6.2), this subject will be considered as an Enrollment Failure.

Randomization will be conducted using Interactive Response Technology (IRT) and treatment will be assigned according to a randomization scheme generated by the Sponsor's unblinded biostatistician. The person generating the randomization scheme will not be involved in the collection, review, and/or analysis of study data before database lock and unblinding.

### **6.2 Study Product Administration**

#### **6.2.1 Pre-procedure Medication**

Prior to LYR-210 administration or the sham procedure, all subjects will receive topical anesthetic and decongestant sprays for endoscopic assessment. Subjects will further receive anesthetic and decongestant soaked cottonoids or pledgets in each nostril to prepare the middle meatus for the study product insertion procedure.

#### **6.2.2 Study Product Preparation**

LYR-210 and the sham procedure article will be provided to the study site as described in Section 7.2.1. Preparation of LYR-210 or the sham procedure article should be performed in accordance with the instructions of use (IFU) provided in a separate document and should not start until the subject has been prepared and is ready for the administration procedure.

#### **6.2.3 Study Product Administration**

LYR-210 is designed to be administered intranasally under endoscopy visualization. Subjects who are assigned to either dose of LYR-210 will have LYR-210 administered bilaterally into the middle meatus. Subjects who are assigned to the sham procedure arm, will undergo bilateral mock administration (i.e., sham procedure), consisting of a bilateral insertion of an applicator

(without LYR-210 loaded) into the middle meatus until the applicator tip touches the ethmoid bulla for a minimum of 20 seconds, followed by withdrawal of the applicator. To maintain subject blinding to the treatment assignment, each subject will wear an eye mask (i.e., blindfold) at the time of the LYR-210 administration/sham procedure. An independent, unblinded case manager may be present during day 1 visit to assist product administration.

Following administration procedure, all enrolled subjects will rest for at least 1 hour and be monitored to ensure there is no epistaxis that requires medical attention.

#### **6.2.4 Enrollment Failure**

The Investigator will be allowed up to two attempts at LYR-210 administration or at the sham procedure per side. A treatment attempt is defined as that an applicator of a LYR-210 or sham article is inserted to a subject's left or right nostril for an attempt of investigational product administration. If the Investigator is unable to administer LYR-210 bilaterally or perform sham procedure successfully into both middle meatuses of a subject, the Investigator will remove any LYR-210 already administered and treat the subject with any appropriate therapy, if necessary. The subject will be considered as an **Enrollment Failure** as described in Section 6.1. Subjects will be followed within 7 ( $\pm$  2) days via telephone for AE and concomitant medication assessment.

#### **6.2.5 End of Day 1 Visit**

Prior to discharge at Day 1 visit, all enrolled subjects will be provided with clear instructions and the following reminders:

- That they are currently enrolled in an investigational study for up to 12 months.
- To avoid nose blowing for the rest of the day post-procedure.
- To wipe or gently blow their nose during the treatment stage.
- To sneeze with mouth open to avoid over-pressurization to the nose.
- To call the study clinic if they have any unexpected epistaxis.
- To call the study clinic immediately should the subject experience severe discomfort or if LYR-210 falls out of the nose. If this occurs - instruct subject to retain the depot (place in a plastic bag/vial and store in a freezer if possible) and return to the clinic at the next clinic visit.

### **6.3 Blinding**

Except for the cases of spontaneous depot dislodgement, subjects should remain blinded to their treatment assignment (LYR-210 or sham) until the final study database is locked. To maintain subject blinded (LYR-210 or sham), each subject will wear an eye mask (i.e., blindfold) at the time of the LYR-210 administration/sham procedure and at all post Day 1 visits (scheduled or unscheduled) if an endoscopy assessment is performed.

The investigational site staff will be blinded regarding the impending treatment assignment until after a study subject has completed all baseline assessments required on Day 1 visit (Section 8.1) prior to randomization assignment. After randomization assignment, the investigational site staff, including the Investigator and study coordinator, will be unblinded as to whether the subjects receive LYR-210 administration or sham procedure. The study clinic staff, including the Investigator and study coordinator, will be blinded as to the dose administered to subjects receiving LYR-210.

The Sponsor will be blinded to subjects' study treatment assignments until database lock for the primary data analysis after all enrolled subjects have completed Week 28 visit or withdrawn from study, whichever comes first.

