#### **6.4.4 Rescue Concomitant Medications and Treatment**

The following rescue medications are recommended in the event of an acute exacerbation of the following conditions that result in the subject contacting the Investigator who determines an initiation of rescue therapy:

- Any time during the 24-week treatment stage:
  - After a clinic visit and per Investigator's judgment, antibiotics for sinus infection.
  - After a clinical visit and evaluation for worsening or uncontrolled severe CS symptoms, the Investigator using his/her best judgement may give a course of oral corticosteroids. Typical indications include persistent sinus infection after an initial course of antibiotics while starting another course of antibiotics, uncontrolled sinus inflammation not responding to an INCS, or a flare-up of asthma. The rationale for the use of oral corticosteroid must be recorded.
- After the Week 4 visit only:
  - For acute allergic symptoms: non-sedating oral antihistamine such as loratadine (10 mg per day) or equivalent.
  - For severe acute nasal blockage (score of 2 or more over the past 3 days): a course of oxymetazoline spray for a maximum of 3 consecutive days and a total maximum of 10 days during the treatment period. Oxymetazoline cannot be used within 24 hours before MRI assessments.
  - For worsening CS symptoms: intranasal MF sprays with dose and duration per Investigator's recommendation.
  - For worsening or uncontrolled severe CS symptoms: ESS as rescue treatment per Investigator's recommendation.

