#### **10.6.2.3 Time-to-Treatment Failure**

The third key secondary endpoint is the time-to-treatment failure. A treatment failure is defined as, after subject enrollment, the subject being recommended by treating physician for oral corticosteroid or ESS due to worsening of CS symptoms, or the subject complaint of persistent CS symptoms with an average CS7DA4S score over the preceding 30 days greater than or equal to the baseline CS7DA4S score. Time to treatment failure will be analyzed using a Cox proportional hazards model with fixed effects for available baseline CS7DA4S score, treatment group and the randomization stratification variables. Kaplan-Meier plots of time to treatment failure will be presented for each treatment group. There will be no imputation of missing data; subjects without the event through Week 24 will be censored at the end of their follow-up period. This analysis will be performed using subjects in the ITT analysis set with available data and repeated using subjects in the PP set analysis set with available data.

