15.2.1.3. Time-to-Treatment Failure

Time-to-treatment failure, in days, will be derived as:

$$\text{Time (days)} = \text{date of treatment failure} - \text{treatment start date} + 1$$

Where treatment failure is defined as:

- after subject enrollment, the subject being recommended by treating physician for oral corticosteroid or ESS due to worsening of CS symptoms as collected on the Follow-up eCRF

OR

- the subject complaining of persistent CS symptoms, i.e., has an average CS7DA4S score over the preceding 30 days greater than or equal to the baseline CS7DA4S score as defined by ██████████ Biostatistics.
 - The earliest timepoint at which to calculate this score is Day 31. For each day post-Day 30, the average CS7DA4S over the preceding 30 days will be derived and compared to the baseline CS7DA4S score
 - The average CS7DA4S for at least 21 of the preceding 30 days should be available for this derivation.

Subjects without the event will be censored at their follow-up period. That is, should a subject reach Week 24 without having met the criteria for the time-to-treatment failure, the subject will be censored at the date of the Week 24 visit; should a subject discontinue early from the study before Week 24 without having met the criteria for the time-to-treatment failure, the subject will be censored at the date of discontinuation from study.

Time-to-treatment failure will be derived at different timepoints: Weeks 2 (15 days), 4 (29 days), 8 (57 days), 12 (85 days), 16 (113 days), 20 (141 days) and 24 (169 days). These timepoints are independent of the scheduled visits.

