15.2.4.3. Analysis of Time-to-Treatment Failure

The number and percentage of subjects with and without treatment failure will be presented based on the ITT analysis set. For subjects without treatment failure, the censoring reason will be summarized. Time-to-treatment failure (days) will be analyzed for the ITT analysis set using a Cox proportional hazards model with fixed effects for baseline CS7DA4S score, treatment group and the stratification variables (nasal allergy and nasal polyps). The Hazard ratio of each LYR-210 treatment group vs. the Sham treatment group, its 90% CI and p-values will be presented.

Additionally, Kaplan-Meier results will be displayed for the 25%, 50% and 75% quartiles, along with Kaplan-Meier estimates of probability of treatment failure at different timepoints: Weeks 2, 4, 8, 12, 16, 20 and 24. These timepoints are independent of the scheduled visits. Kaplan-Meier plots of time-to-treatment failure will be produced for each treatment group.

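### Time to treatment failure merges recommendations by a physician who knows LYR-210 versus sham with a subject-blinded diary criterion, and the SAP text specifies no analysis that separates them

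*Protocol*

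**What the plan says.** **Who is blinded.** Protocol 6.3 states that site staff, including the Investigator and coordinator, "will be unblinded as to whether the subjects receive LYR-210 administration or sham procedure" once assignment is made, although they "will be blinded as to the dose administered to subjects receiving LYR-210". For subjects: "Except for the cases of spontaneous depot dislodgement, subjects should remain blinded to their treatment assignment".

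**What counts as failure.** Protocol 10.6.2.3: "The third key secondary endpoint is the time-to-treatment failure". SAP 15.2.1.3 allows two routes to an event:
- Physician route: "the subject being recommended by treating physician for oral corticosteroid or ESS due to worsening of CS symptoms as collected on the Follow-up eCRF".
- Diary route, met when a participant "has an average CS7DA4S score over the preceding 30 days greater than or equal to the baseline CS7DA4S score as defined by" the biostatistics group. At least 21 of the 30 days must be available, and the first day on which this can be assessed is Day 31.

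**Who recommends rescue.** Under Protocol 6.4.4, after a visit and evaluation, "the Investigator using his/her best judgement may give a course of oral corticosteroids", with the rationale recorded. ESS as rescue is listed only after the Week 4 visit and follows the Investigator's recommendation.

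**What is analysed.** SAP 15.2.4.3: "The number and percentage of subjects with and without treatment failure will be presented based on the ITT analysis set". Censoring reasons are summarized for subjects without failure. One Cox model is fitted to the merged event, with Kaplan-Meier quartiles, plots and failure probabilities at Weeks 2, 4, 8, 12, 16, 20 and 24. Protocol 10.6.2.3 repeats the analysis in the PP set. Protocol 10.6.2 tests each dose against sham at one-sided 0.05; SAP 7.8 describes all p-values as nominal. SAP 3.3 drops the separate endpoint on need for medical or surgical treatment because its data were not collected.

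**The concern.** The first route to failure is a discretionary recommendation, and receipt of the treatment is not required. Under the rescue rules it comes from someone who knows whether the subject has a depot. A physician who knows that a subject had only a sham may recommend steroid or surgery sooner. Masking of dose protects the 2500 versus 7500 µg comparison, but not either dose versus sham, which is the comparison tested.

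The bias would run in the direction of the one-sided test. Because the SAP text describes only the merged event, a reader of the results could not tell whether a favourable hazard ratio came from the blinded diary or from the unblinded recommendations. Of the three key secondary endpoints, this is the only one with such a component: the Week 24 symptom score comes from the diary, and the Zinreich score is read by an imaging vendor.

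**Working it through.** **1. The plan's own figures.** The documents give no event rate, hazard ratio or power for this endpoint. Their one power figure is 73% for the Week 4 primary endpoint (21 per group, difference 3.00 − 1.30 = 1.70, SD 2.4, one-sided 0.05). It reproduces at 0.730 for one dose versus sham (noncentral t, 40 df), but does not bear on this point.

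**2. Timing, from the documents alone.** The diary criterion is first assessable on Day 31. SAP 15.2.1.3 sets Week 2 at 15 days and Week 4 at 29 days. Both precede Day 31, so every failure counted in those two Kaplan-Meier estimates must be a physician recommendation.

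**3. Apparent hazard ratio with no true effect.** Assume constant hazards, equal diary failure in both arms, and recommendations *k* times as frequent in sham. Let *s* be the physician-driven share of events.
- If *s* is the share in the LYR-210 arm: HR = 1 / [(1 − s) + s·k].
- If *s* is the share in the sham arm: HR = (1 − s) + s/k.

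| s | k | s in LYR-210 arm | s in sham arm |
|---|---|---|---|
| 0.50 | 1.5 | 1/(0.50 + 0.75) = 0.80 | 0.50 + 0.33 = 0.83 |
| 0.50 | 2.0 | 1/(0.50 + 1.00) = 0.67 | 0.50 + 0.25 = 0.75 |
| 0.25 | 1.5 | 1/(0.75 + 0.375) = 0.89 | 0.75 + 0.17 = 0.92 |

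Both formulas need *s* constant over time. Before Day 31, *s* = 1 and both reduce to 1/k: 0.67 at k = 1.5 and 0.50 at k = 2.

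**4. Rejection rate with no true effect.** This was a log-rank simulation standing in for the Cox model: 23 versus 23 subjects (about 70/3), 169 days, one-sided 0.05, 40,000 runs per scenario. Diary failure by Week 24 is equal in both arms at 10% or 20%, and diary scores are assumed unaffected by rescue.

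| Recommended, sham vs LYR-210 | Merged, diary 10% | Merged, diary 20% | Diary only |
|---|---|---|---|
| 15% vs 15% | 5% | 5% | 5% |
| 20% vs 10% | 18% | 15% | 5–6% |
| 25% vs 10% | 29% | 22% | 5% |
| 30% vs 10% | 40% | 32% | 5–6% |
| 40% vs 10% | 65% | 54% | 5–6% |

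The 20% versus 10% row is closest to k = 2: the hazard ratio for recommendation is ln(0.80)/ln(0.90) = 2.1. The lower rows need larger imbalances than step 3 uses.

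**5. What a diary-only analysis could show.** The same assumptions give about 5 (diary 10%) to 9 (diary 20%) diary events per comparison. With SE(log HR) = 2/√d and an assumed true HR of 0.5 (log HR −0.693):
- d = 5: SE 0.894, power about 19%, chance of an estimate above 1 about 22%.
- d = 9: SE 0.667, power about 27%, chance of an estimate above 1 about 15%.

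With no effect, the estimate falls below 1 about half the time.

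**The case against.** **The study is exploratory and p-values are nominal (SAP 7.8).** That answers multiplicity. It does not answer bias in the hazard ratio itself. It does count against any formal condition on a claim. One might want the diary-only hazard ratio to point the same way before failure results are believed. At 5 to 9 events that check would fail a true HR of 0.5 in 15–22% of trials and pass a null effect in about half. This objection stands.

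**Blinded evidence already exists.** Diary scores are analysed through Week 24, including as a key secondary endpoint, with per-protocol, imputation and GEE analyses. This is useful indirect support. It does not show which component drives the failures.

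**Discretion is bounded.** Oral corticosteroid requires a visit, an evaluation and a recorded rationale, and ESS rescue is listed only after Week 4. No blinded assessor, adjudication or numeric threshold is set, so the exposure is reduced but not removed.

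**The diary component is not a clean comparator.** Dislodgement, which only LYR-210 subjects can have, may unblind the subject. If sham subjects are recommended and given rescue more readily, their later diary scores may fall, which pulls the diary result against LYR-210. Censoring at the recommendation is informative. Both points stand and shape the fix.

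**Some readings go too far.** A reader might infer that the components will never be displayed. The SAP leaves output content to table and listing shells that are not in the reviewed documents, and the Protocol synopsis promises individual listings, so only the absence from the SAP text is established. Nor is the treating physician always the Investigator: the failure definition does not exclude an outside physician, although the rescue rules assign these decisions to the Investigator.

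**Conclusion.** The point holds. Recommendations that under Protocol 6.4.4 come from an unblinded Investigator are merged with a largely blinded diary criterion, and the planned analysis as written cannot separate a bias favouring LYR-210 from a drug effect. The Week 2 and Week 4 failure estimates rest wholly on the recommendation component; that follows from the SAP's own days and needs no assumption.

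The size is illustrative, because all rates are assumed. With half of events physician-driven, the apparent hazard ratio under no effect is 0.80–0.83 at 1.5 times the recommendation rate in sham, and 0.67–0.75 at twice, depending on which arm the half describes. With recommendations at 20% versus 10%, the merged test rejects 15–18% of the time instead of about 5%.

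A reader might infer that the result will be biased. The documents show an opportunity for bias and no planned means of detecting it; they do not show that physicians will act on what they know. A reader might also infer from SAP 3.3 that the recommendations were never recorded. SAP 15.2.1.3 names the Follow-up eCRF as their source, so the two sections conflict and the documents do not settle it.

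**What to change.** Specify the following in SAP 15.2.4.3 before unblinding:

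- (a) Tabulate first failure events by component (oral corticosteroid recommendation, ESS recommendation, diary criterion) and arm. This needs no power and shows directly how far the result depends on recommendations.
- (b) Add, as supportive only, a Kaplan-Meier plot and Cox model for time to the diary-defined event, with a stated rule for subjects first recommended for oral corticosteroid or ESS. For example, continue diary follow-up regardless, then repeat with censoring at the recommendation. State that either rule can carry some of the physician's influence.
- (c) Interpret the merged hazard ratio, and the Week 2 and Week 4 estimates in particular, in light of (a) and (b), with no formal same-direction requirement.
- (d) Reconcile SAP 3.3 with SAP 15.2.1.3 on whether the recommendation data were collected; item (a) depends on the answer. Reconcile also the Protocol's wording of the diary route as a subject complaint with the SAP's derivation from the score alone.

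The cost is one table and one model (fitted under each rescue rule), with no new visits or assessors if the Follow-up eCRF holds the recommendations. The drawback is few diary events and wide intervals.
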